3.3 DOSE MODIFICATIONS IN PHASE I (POST CYCLE 1) AND PHASE II

Patients with stable or responding disease may be retreated at the same dose or at a reduced dose level, depending upon the adverse events observed in the current cycle and any adverse events (based on the CTCAE v.4) present on the first day of the next cycle. If multiple toxicities are seen, the dose administered in a subsequent cycle should be based on the most severe toxicity experienced in the current cycle.

Patients who experience toxicity should have laboratory testing at least weekly until the toxicity has resolved.

Toxicities will be graded according to the NCI Common Terminology Criteria for Adverse Events (CTCAE) version 4.0. If multiple toxicities are seen, the toxicity should be based on the most severe toxicity experienced. Toxicities will be defined as any of the following events occurring during treatment with sorafenib and/or everolimus and attributable to one of the study drugs:

- A. Any grade 3 thrombocytopenia, grade 4 anemia, grade 4 neutropenia, or febrile neutropenia of any grade.
- B. Any non-hematologic grade 3 or grade 4 toxicity, excluding alopecia and/or hand/foot reaction.
- C. Failure to recover from grade 3 or 4 toxicities (to grade 1 or less) to be eligible for re-treatment with sorafenib and everolimus within 14 of the last dose of sorafenib and everolimus.

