3.3.1 Within Treatment Cycles

If a patient experiences toxicities during a treatment cycle, the treatment will be immediately suspended until a grade 1 or less toxicity. If the toxicity resolves to less than or equal to grade 1 within 2 weeks, the patient will be retreated at the dose level described in Table **3-2** below. (Refer to Table **3-6** and Table **3-7** for management of everolimus-induced toxicities and Table **3-8**, Table **3-9** and Table **3-10** for management of sorafenib-induced toxicities.) If toxicity persists, the patient should be taken off study.

Two dose reductions are permitted. Doses that are reduced for sorafenib or everolimus related toxicity will not be re-escalated, even if there is minimal or no toxicity with the reduced dose. Patients whose dose has been reduced for adverse events that are subsequently not felt to be related to sorafenib or everolimus may have the dose re-escalated after completion of one cycle with toxicities less than or equal to grade 1. If any patient has further toxicities that would require additional reductions, or if treatment is held for more than 2 consecutive weeks because of ongoing

toxicity, the Study PI will assess if the patient should remain in the study (if the patient has benefited from treatment).

Table 3-2: Dose Modification Table

DOSE LEVEL	SORAFENIB	EVEROLIMUS
1 (starting dose)	400 mg BID 7 days on 7 days off	5 mg daily
-1	400 mg AM dose 200 mg PM dose 7 days on 7 days off	5 mg daily
-2	200 mg AM dose 200 mg PM dose 7 days on 7 days off	5 mg daily

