3.3.1.2 Non-hematologic Toxicity

Dose Modifications

Based on **sorafenib or everolimus** -Related Non-Hematologic Toxicities:

CTCAEv.4 Grade	% of Dose Planned
0-2+	100%+
3*	hold**
4	hold***

+For symptomatic Grade 2 toxicity, the suspect drug dose may be held at the discretion of the local investigator until recovery to CTCAE Grade 0-1, then resume at one dose lower.

*Except nausea/vomiting (unless patients are on optimal antiemetic therapy)

**Hold suspect drug until recovery to CTCAE Grade 0-1 (or to within 1 grade of starting values for pre-existing laboratory abnormalities), and then resume at one dose level lower.

***Hold suspect drug until recovery to CTCAE Grade 0-1 (or to within 1 grade of starting values for pre-existing laboratory abnormalities), and then resume at two dose levels lower.

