3.3.2.2 Monitoring for hepatitis C

The following two categories of patients should be monitored every 4 weeks for HCV reactivation:

- Patients with detectable HCV RNA-PCR test at baseline.
- Patients known to have a history of HCV infection, despite a negative viral load test at baseline (including those that were treated and are considered ‘cured’)

For definition of hepatitis C reactivation and the management guidelines, see Table 3-5 Guidelines for management of hepatitis C.

Table 3-5: Guidelines for management of hepatitis C

HCV reactivation*	
For patients with baseline results: Detectable HCV-RNA, reactivation is defined as: ALT elevation x 5 ULN	Discontinue study drug
For patients with baseline results: Knowledge of past hepatitis C infection with no detectable HCV-RNA, reactivation is defined as: New appearance of detectable HCV-RNA	Discontinue study drug

* All reactivations of hepatitis C are to be recorded as grade 3 (CTCAE v4.0 Metabolic Laboratory/Other: Viral Re-activation), unless considered life threatening by the investigator; in which case, they should be recorded as grade 4 (CTCAE v 4.0 Metabolic Laboratory/Other: Viral Re-activation).

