3.3.8 Management of sorafenib induced skin toxicity

It is common for patients treated with sorafenib to experience skin toxicity (rash/desquamation, hand/foot reaction, etc.). Guidelines for management are specified in the table below.

Table 3-8: Guidelines for management of sorafenib induced skin toxicity

Skin Toxicity Grade	Occurrence	Suggested Dose Modification
Grade 1: Numbness, dysesthesia, paresthesia, tingling, painless swelling, and erythema or discomfort of the hands or feet which does not disrupt the patient's normal activities.	Any occurrence	Continue treatment with sorafenib and consider topical therapy for symptomatic relief.
Grade 2: Painful erythema and swelling of the hands or feet and/or discomfort affecting the patient's normal activities.	First occurrence	Continue treatment with sorafenib and consider topical therapy for symptomatic relief. If no improvement within 7 days, see below.
	No improvement within 7 days or 2 nd occurrence	Interrupt sorafenib treatment until toxicity resolves to Grade 0-1. When resuming treatment, decrease sorafenib dose by one dose level.
	Third occurrence	Interrupt until resolved to grade 0-1. When resuming treatment, decrease dose by two dose levels (from the starting dose).
Grade 3: Moist desquamation, ulceration, blistering or severe pain of the hands or feet, or severe discomfort that causes the patient to be unable to work or perform activities.	First occurrence	Interrupt sorafenib treatment until toxicity resolves to Grade 0-1. When resuming treatment, decrease sorafenib by one dose level.
	Second occurrence	Interrupt until resolved to grade 0-1. When resuming treatment, decrease dose by two dose levels (from the starting dose).
	Third occurrence	Discontinue sorafenib treatment.

Table 3-9: Dose Modifications for Sorafenib-Associated Toxicity¹

Toxicity	Grade 1	Grade 2	Grade 3*	Grade 4*
Non-hematologic	Continue at the same dose level.	Continue at the same dose level.	Withhold dose until toxicity is < 1. When resuming treatment reduce dose by one dose level.	Discontinue treatment.
Hematologic	Continue at the same dose level.	Continue at the same dose level.	Withhold dose until toxicity is grade <2. When resuming treatment reduce dose by one dose level.	Withhold dose until toxicity is grade <2. When resuming treatment reduce dose by two dose levels.

¹ See separate suggestions for dose modification due to hand-foot skin reactions.

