Hemorrhage: An increase in the risk of bleeding may occur following sorafenib administration. The incidence of severe bleeding events is uncommon. If any bleeding event necessitates medical intervention, it is recommended that permanent discontinuation of sorafenib should be considered.

Wound healing complications: No formal studies of the effect of sorafenib on wound healing have been conducted. In patients undergoing major surgical procedures, temporary interruption of sorafenib therapy is recommended for precautionary reasons. There is limited clinical experience regarding the timing of reinitiation of therapy following major surgical intervention. Therefore, the decision to resume sorafenib therapy following a major surgical intervention should be based on clinical judgment of adequate wound healing.

Cardiac Ischemia and/or Infarction: In the Phase 3 Advanced RCC study (TARGETS), the incidence of treatment-emergent cardiac ischemia/infarction events was higher in the sorafenib group (2.9%) compared with the placebo group (0.4%). Patients with unstable coronary artery disease or recent myocardial infarction were excluded from this study. Temporary or permanent discontinuation of sorafenib should be considered in patients who develop cardiac ischemia and/or infarction.

Gastrointestinal perforation: Gastrointestinal perforation is an uncommon event and has been reported in less than 1% of patients taking sorafenib. In some cases this was not associated with apparent intra-abdominal tumor. Sorafenib therapy should be discontinued in patients with GI perforation.

Effects on ability to drive and use machines: No studies on the effects of sorafenib on the ability to drive or use machines have been performed. There is no evidence that sorafenib affects the ability to drive or operate machinery.

Patients with Hepatic Impairment: *In vitro* and *in vivo* data indicate that sorafenib is primarily metabolized by the liver. Systemic exposure and safety data were comparable in patients with

Child-Pugh A and B hepatic impairment. Sorafenib has not been studied in patients with Child-Pugh C hepatic impairment. No dose adjustment is necessary when administering sorafenib to patients with Child-Pugh A and B hepatic impairment.

Patients with Renal Impairment: Sorafenib has not been studied in patients with severe renal impairment (CrCl <30 mL/min) or in patients undergoing dialysis.

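### Sorafenib dosing rules in section 3.3 omit the GI perforation stop given in section 10.1.12.1, and disagree with each other on grade 4 non-hematologic toxicity

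*Combined protocol and SAP*

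**What the plan says.** The GI perforation warning sits among the special warnings for sorafenib in section 10.1.12.1 and reads "Sorafenib therapy should be discontinued in patients with GI perforation". It sets no grade threshold. The adverse reaction table in section 10.1.12 marks GI perforation as a reaction that can be life-threatening or fatal.

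Dosing after toxicity is governed by section 3.3, which opens by saying that patients with stable or responding disease "may be retreated at the same dose or at a reduced dose level". Within a cycle, section 3.3.1 suspends treatment and directs retreatment at a Table 3-2 level if the toxicity settles to grade 1 or less within two weeks. It sends sites to Tables 3-8, 3-9 and 3-10 "for management of sorafenib-induced toxicities".

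- **Grade 3 non-hematologic.** Section 3.3.1.2 holds the suspect drug until recovery, "and then resume at one dose level lower". Table 3-9, which is specific to sorafenib, says "Withhold dose until toxicity is < 1. When resuming treatment reduce dose by one dose level".
- **Grade 4 non-hematologic.** Section 3.3.1.2 holds until recovery, "and then resume at two dose levels lower". Table 3-9 says "Discontinue treatment".

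The exceptions written into these two rules are nausea and vomiting (3.3.1.2), hand-foot skin reaction (Table 3-9, footnote 1), and a short list covering fever or chills, transaminases, hyperlipidemia or hyperamylasemia, leukopenia and lymphopenia (Table 3-9, asterisk footnote). Perforation is not named in section 3.3 or in the removal criteria of section 3.7.

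**The concern.** A site that follows the dosing section to the letter can restart sorafenib after an event for which the protocol's own drug section says to stop it. The stop instruction is also easy to miss. It stands under a numbered heading about laboratory abnormalities, and section 3.3 does not refer to it.

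The grade 4 rules raise a second, independent problem. Two rules in the same section give different sorafenib instructions for the same grade, whatever the event, and no text says which prevails.

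The stake is the safety of individual patients.

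**Working it through.** No alpha, power or event count enters this point. The check sets the rules side by side, works out the doses they lead to, and bounds how often the perforation case could arise.

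**Rules side by side (sorafenib, drug-related non-hematologic toxicity)**

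| Event | 10.1.12.1 | 3.3.1.2 | Table 3-9 |
|---|---|---|---|
| GI perforation, grade 3, recovered in time | Discontinue | Resume one level lower | Resume one level lower |
| GI perforation, grade 4, recovered in time | Discontinue | Resume two levels lower | Discontinue |
| Any other grade 4 event, recovered in time | No general rule | Resume two levels lower | Discontinue |

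At grade 3 the two dosing rules agree with each other and differ from the warning. At grade 4 they differ from each other, and for perforation Table 3-9 agrees with the warning. Recovery means grade 0-1 in 3.3.1.2; Table 3-9 writes it as below 1.

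**Does section 3.3 ever override the grade rule for a named event?** Yes. Hepatitis C reactivation is recorded as grade 3 unless life-threatening, and Table 3-5 gives "Discontinue study drug" rather than a dose reduction (section 3.6.1.6 names everolimus). The stops for grade 4 hypertension (Table 3-10) and grade 4 pneumonitis (Table 3-6) are weaker comparators. The first matches what Table 3-9 already says for grade 4, and the second concerns everolimus-induced pneumonitis. A perforation line would still fit the way section 3.3 is built.

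**Which grade 4 rule is the outlier?** Table 3-9 discontinues sorafenib, and Table 3-7 discontinues everolimus, for grade 4 non-hematologic toxicity. Section 3.3.1.2 alone resumes.

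**Doses (Table 3-2; sorafenib on days 1-7 and 15-21, so 14 dosing days per 28-day cycle)**

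- Starting level: (400 + 400) × 14 = 11,200 mg per cycle.
- Level -1, after a recovered grade 3 event: (400 + 200) × 14 = 8,400 mg; 8,400 / 11,200 = 75%.
- Level -2, after a recovered grade 4 event under 3.3.1.2: (200 + 200) × 14 = 5,600 mg; 5,600 / 11,200 = 50%. Under Table 3-9: 0 mg.

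**Frequency bound for the perforation case.** Section 10.1.12.1 reports perforation in less than 1% of patients taking sorafenib. Assume that this rate carries over to the combination with everolimus.

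- All of phase II: fewer than 0.01 × 82 = 0.82 expected events of any grade.
- Group B: fewer than 0.01 × 32 = 0.32.

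The conflict needs more than a perforation. The event must be drug-related and either grade 3 with recovery in time, or grade 4 with recovery and handling under 3.3.1.2. The documents do not give these shares, so there is an upper bound and no point estimate.

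**Grade 4 toxicity in general.** This part does not depend on perforation being rare. Section 10.1.12.1 reports grade 4 clinical pancreatitis in 2 of 451 sorafenib-treated patients in the renal cell trial (2 / 451 = 0.4%), so such events do occur. That figure does not state attribution and covers one event type, so it is not an estimate of the overall grade 4 rate.

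**The case against.** The best defence is that a specific warning governs a generic default. The perforation warning is current text of the same protocol, so one can read it as controlling and leave the grade rules for everything else. Section 3.3 opens permissively, section 3.7.1.2 lets the investigator stop for unacceptable toxicity, and section 3.7.1.4 covers illness that makes further therapy impossible. The two-week limit in 3.3.1 and the 21-day limit in 3.7.1.5 remove most slow recoveries, although 3.3.1 also lets the study PI decide on longer holds. On this view all that is missing is a cross-reference.

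Most of that stands as a limit on practical impact. A reader might infer that the protocol gives flatly opposite orders for perforation. The documents do not support that, because no line in section 3.3 mentions restarting after perforation and the specific-over-general reading is available. The defence does not remove the defect, however. The within-cycle rule in 3.3.1 is worded as a directive, its pointer for sorafenib toxicity leads to Table 3-9 and not to section 10, and none of the discretionary provisions requires stopping.

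A reader might also infer that section 10.1.12.1 forbids ever resuming sorafenib. It does not say so. Nearby warnings use permanent, or temporary or permanent, where duration is meant; the perforation warning uses neither word. Permanent cessation is a plausible reading, but it is an inference.

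Finally, it is fair to say that the grade 4 mismatch is not a perforation finding. It applies to every sorafenib-related grade 4 non-hematologic event and should be judged separately.

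**Conclusion.** Both parts are wrong as written, and both concern patient safety only.

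1. The operative sorafenib rules lack the perforation stop that section 10.1.12.1 calls for. After a drug-related grade 3 perforation that recovers in time, they lead to a restart at 75% of the starting dose. The chance per patient is below 1%, on the assumption that the quoted sorafenib rate applies to the combination. A restart is unlikely in practice, but nothing in the dosing or removal sections requires stopping.
2. Independently, section 3.3 contradicts itself on grade 4 non-hematologic toxicity from sorafenib: 50% of the starting dose under 3.3.1.2, none under Table 3-9. The documents do not allow a frequency to be put on this.

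The number of patients still exposed is unknown. Section 2.4 marks Groups A and C as closed but not Group B, and section 9.4 says that subjects at non-NCI sites were off treatment at Amendment C.

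It would be a mistake to infer any effect on PFS3, PFS6, error rates or sample size; nothing in the documents supports one. The correction is worth making because the event can be fatal and the edit is small.

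**What to change.** - Add to section 3.3.1.2 and to Table 3-9: GI perforation, any grade: discontinue sorafenib (see the GI perforation warning in 10.1.12.1); the grade-based resume rules do not apply.
- In section 3.3.1.2, change the grade 4 non-hematologic rule for sorafenib to discontinue, so that it matches Table 3-9.

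The perforation line points to the warning without crediting it with a ban on resumption that it does not state.

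The cost is a short protocol amendment: one line in two places and one edit to the grade 4 rule, with no added patients or procedures. The downside is that sorafenib rechallenge is lost after a perforation and after a recovered grade 4 non-hematologic event. Section 10.1.12.1 and Table 3-9, respectively, already advise against these.

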10.1.12.2 Interaction with Other Medications

Drug-Drug Interactions: Caution is recommended when administering sorafenib together with compounds that are metabolized/ eliminated predominantly by the UGT1A1 pathway (e.g. irinotecan):

- **CYP3A4 inducers:** There is no clinical information on the effect of CYP3A4 inducers on the pharmacokinetics of sorafenib. Inducers of CYP3A4 activity (e.g. rifampicin, *Hypericum perforatum* also known as St. John's wort, phenytoin, carbamazepine,

phenobarbital, and dexamethasone) may increase metabolism of sorafenib and thus decrease sorafenib plasma concentrations.

- **CYP3A4 inhibitors:** Ketoconazole, a potent inhibitor of CYP3A4, administered once daily for 7 days to healthy male volunteers did not alter the mean AUC of a single 50 mg dose of sorafenib. Therefore, clinical pharmacokinetic interactions of sorafenib with CYP3A4 inhibitors are unlikely.
- **CYP2C9 substrates:** The possible effect of sorafenib on the metabolism of the CYP2C9 substrate warfarin was assessed indirectly by measuring PT/INR. The mean changes from baseline in PT-INR were not higher in sorafenib patients compared to placebo patients, suggesting that sorafenib did not inhibit warfarin metabolism *in vivo*. However, patients taking warfarin should have their INR checked regularly.
- **CYP isoform-selective substrates:** Concomitant administration of midazolam, dextromethorphan and omeprazole, which are substrates of cytochromes CYP3A4, CYP2D6 and CYP2C19, respectively, following 4 weeks of sorafenib administration did not significantly alter the exposure of these agents. This indicates that sorafenib is neither an inhibitor nor a clinically meaningful inducer of these cytochrome P450 isoenzymes.
- **Combination with other anti-neoplastic agents:** In clinical studies, sorafenib has been administered together with a variety of other antineoplastic agents at their commonly used dosing regimens, including gemcitabine, oxaliplatin, doxorubicin, and irinotecan. Sorafenib had no effect on the pharmacokinetics of gemcitabine or oxaliplatin. Concomitant treatment with sorafenib resulted in a 21% increase in the AUC of doxorubicin. When administered with irinotecan, whose active metabolite SN-38 is further metabolized by the UGT1A1 pathway, there was a 67-120% increase in the AUC of SN-38 and a 26-42% increase in the AUC of irinotecan. The clinical significance of these findings is unknown. However, caution is recommended when administering sorafenib with doxorubicin and with compounds that are metabolized/eliminated predominantly by the UGT1A1 pathway (e.g. irinotecan).
- **Warfarin:** Infrequent bleeding events or elevations in the International Normalized Ratio (INR) have been reported in some patients taking warfarin while on sorafenib therapy. Patients taking warfarin concomitantly should be monitored regularly for changes in prothrombin time, INR and for clinical bleeding episodes.

10.1.12.3 Pregnancy and Lactation

Pregnancy: Women should avoid becoming pregnant while on therapy. Women of childbearing potential must be apprised of the potential hazard to the fetus, which includes severe malformation (teratogenicity), failure to thrive and fetal death (embryotoxicity). Sorafenib should not be used during pregnancy. Prescribers may only consider it to be used, if the potential benefits justify the potential risks to the fetus.

- There are no adequate and well-controlled studies in pregnant women using sorafenib. Studies in animals have shown reproductive toxicity including malformations. In rats, sorafenib and its metabolites were demonstrated to cross the placenta and sorafenib is anticipated to inhibit angiogenesis in the fetus.

- Women should avoid becoming pregnant while on therapy. Women of childbearing potential must be apprised of the potential hazard to the fetus, which includes severe malformation (teratogenicity), failure to thrive and fetal death (embryotoxicity).
- Sorafenib should not be used during pregnancy. Prescribers may only consider it to be used, if the potential benefits justify the potential risks to the fetus.
- In animals, sorafenib has been shown to be teratogenic and embryotoxic. Adequate contraception should be used during therapy and for at least 2 weeks after completion of therapy.

Breastfeeding should be discontinued during sorafenib therapy.

- It is not known whether sorafenib is excreted in human milk. In animals, sorafenib and/or its metabolites were excreted in milk. Because many drugs are excreted in human milk and because the effects of sorafenib on infants have not been studied, woman should discontinue breastfeeding during sorafenib treatment.

Effects on fertility: Results from animal studies indicate that sorafenib can impair male and female fertility.

10.1.13 Clinical Pharmacokinetic Properties:

After administration of sorafenib tablets, the mean relative bioavailability is 38-49% when compared to an oral solution. The mean elimination half-life of sorafenib is approximately 25-48 hours. Multiple dosing of sorafenib for 7 days resulted in a 2.5-to 7-fold accumulation compared to single dose administration.

Steady-state plasma sorafenib concentrations are achieved within 7 days, with a peak-to-trough ratio of mean concentrations of less than 2.

